3.4 Safety Endpoints

The following endpoints will be included in the safety analyses:

- Treatment emergent adverse events;
- Serious adverse events;
- Adverse events of special interest;
- Adverse events leading to discontinuation of study drug;
- Vital signs and laboratory tests.

4.0 Analysis Populations

The following population sets will be used for the analyses.

Intent-to-Treat (ITT) Populations

The ITT population for the 12-week double blind induction period (Part 1) (denoted by **ITT1**) includes all randomized subjects who received at least one dose of double-blind study drug during Part 1. The ITT1 population will be used for all efficacy and baseline analyses for Part 1.

For ITT1 population, subjects will be included in the analysis according to the treatment groups that they were randomized to.

The ITT population for the 12-week open-label induction period (Part 2) (denoted by **ITT2**) includes all subjects who have received at least one dose of study drug in Part 2. The ITT2 population will be used for all efficacy and baseline analyses for Part 2.

The ITT population 3 (**ITT3**) includes all subjects who have received at least one dose of study drug in the Part 3.

Per-Protocol Population

The Per-Protocol (PP) population represents a subset of the ITT population, consisting of subjects that did not have a major protocol deviation. Major protocol deviations leading to exclusion from the PP population will be identified prior to database lock.

For **PP** population, subjects will be included in the analysis according to the treatment groups that they were randomized to.

Safety Populations

The safety population for Part 1 (denoted by **SA1**) includes all subjects who received at least one dose of the study drug in Part 1.

The safety population for Part 2 (denoted by **SA2**) includes all subjects who received at least one dose of the study drug in Part 2.

The safety population for Part 3 (denoted by **SA3**) includes all subjects who received at least one dose of the study drug in Part 3.

The safety population for subjects who receive upadacitinib in Part 1 or Part 2 and enrolled in Part 3 (denoted by **SA4**) is a subset of SA3 which includes Cohort 2/Cohort 3 of SA3, defined as subjects who received upadacitinib in Part 1 or Part 2 and received at least one dose of study drug in Part 3.

The all upadacitinib safety population (**SA-UPA**) includes all subjects who received at least one dose of upadacitinib in Part 1 or Part 2 or Part 3.

For the safety populations, subjects are assigned to a treatment group based on the "as treated" treatment group, regardless of the treatment randomized. The "as treated" will be determined by the most frequent dose regimen received in the analysis period.

5.0 Subject Disposition

A summary of subject accountability will be provided where the number of subjects in each of the following categories will be summarized for each treatment group for Part 1, for overall for Part 2 and for each cohort for Part 3:

- Subjects randomized in Part 1;
- Subjects who took at least one dose of study drug (Part 1, Part 2 and Part 3);
- Subjects who completed protocol-specified treatment (Part 1, Part 2 and Part 3);
- Subjects who prematurely discontinued study drug (Part 1, Part 2 and Part 3);
- Subjects who prematurely discontinued from study (Part 1, Part 2 and Part 3).

Number and percentage of subjects who discontinued study drug and who withdrew from the study will be summarized by reason (primary reason and all reasons) for each treatment group within Part 1, for overall for Part 2 and for each cohort within Part 3. Subjects with multiple reasons for premature discontinuation will be counted once in the calculation of the number and percentage of total discontinuations.

In addition, subjects who reported at least one of the protocol deviation categories ([Appendix A](#)) will be summarized for each treatment group.

6.0 Study Drug Duration and Compliance

For the safety populations (SA1, SA2 and SA3), duration of treatment will be summarized for each treatment group for Part 1 (SA1), for overall for Part 2 (SA2) and for each cohort for Part 3 (SA3). Duration of treatment is defined for each subject as last dose date minus first dose date + 1. Duration of treatment will be summarized for each treatment group using the number of subjects treated, mean, standard deviation, median, minimum, and maximum. In addition, the number and percentage of subjects in each treatment duration interval (≥ 2 weeks, ≥ 4 weeks, ≥ 6 weeks, ≥ 8 weeks, ≥ 10 weeks, ≥ 12 weeks) will be summarized.

Treatment compliance will be summarized by treatment group in Part 1, for overall in Part 2 and by cohort in Part 3. Treatment compliance is defined as the number of tablets actually taken divided by the number of tablets that should have been taken. Percent compliance will be summarized.

7.0 Demographics, Baseline Characteristics, Medical History, and Prior/Concomitant Medications

Demographics, baseline or disease characteristics, medical history, and prior and concomitant medications will be summarized for the ITT1 population overall and by treatment group, and overall for ITT2. Categorical variables will be summarized with the number and percentage of subjects; percentages will be calculated based on the number of non-missing observations. Continuous variables will be summarized with descriptive statistics (number of non-missing observations, mean, standard deviation, median, minimum, and maximum).

7.1 Demographics and Baseline Characteristics

Demographic/vital Signs

- Sex (Male, Female)
- Age (Years)
- Age Category (≥ 18 years - < 40 years, ≥ 40 years - < 65 years, ≥ 65 years)
- Ethnicity (Hispanic/Latino, Non-Hispanic/Latino)
- Race category (White, Black or African American, American Indian or Alaska Native, Native Hawaiian or Other Pacific Islander, Asian, Multiple)
- Geographic Region category 1 (US, ex-US)
- Geographic Region category 2 (as defined in [Appendix J](#))
- Tobacco/Nicotine Use (currently smokes, ex-smoker, never smoked, unknown)
- Alcohol use (current drinker, former drinker, non-drinker, unknown)
- Body weight (kg) – overall and by sex
- Body Mass Index (BMI, kg/m^2)

- BMI category
 - Underweight [$< 18.5 \text{ kg/m}^2$]
 - Normal [≥ 18.5 and $< 25 \text{ kg/m}^2$]
 - Overweight [≥ 25 and $< 30 \text{ kg/m}^2$]
 - Obese [$\geq 30 \text{ kg/m}^2$]
- Body temperature ($^{\circ}\text{C}$)
- Height (cm)
- Pulse (bpm)
- Systolic and diastolic blood pressure (mmHg)

Patient Reported Outcome Questionnaires at Baseline

- IBDQ total and domain scores
- WPAI-CD - 4 sub-scores
- CSS
- FACIT-F and its components
- EQ-5D-5L - Index score and VAS
- SF-36 - 8 domain scores, PCS and MCS

Other Baseline Characteristics

- CDAI
- Average Daily very soft or liquid SF
- Average Daily AP score
- SES-CD
- SES-CD category (< 15 , ≥ 15)
- Crohn's Disease Duration (years)
- Crohn's Disease Duration category (≤ 5 years, > 5 years)
- CGHAS/IGHAS Score
- Baseline CD-related corticosteroid use (yes, no)

- Baseline CD-related immunosuppressant use (yes, no)
- Baseline CD-related aminosalicylates use (yes, no)
- Prior biologic use/failure history
 - Prior biologic failure history ($\leq 1, 2, \geq 3$)
 - Prior failure to anti-TNF agent (yes, no)
 - Prior vedolizumab/natalizumab failure (yes, no)
 - Prior ustekinumab failure (yes, no)
- hs-CRP (mg/L)
- hs-CRP category ($< 5, \geq 5$ mg/L)
- FCP ($\mu\text{g/g}$)
- FCP category ($\leq 250 \mu\text{g/g}, > 250 \mu\text{g/g}$)
- Draining fistulas (yes, no)
- Non-draining fistulas (yes, no)
- Anal fissures (yes, no)
- CD Location Per SES-CD (ileal, ileocolonic, colonic; [Appendix H](#))
- EIM (yes, no)

In addition, clinical tests at baseline such as TB test, pregnancy test and electrocardiogram assessment will be summarized. Crohn's Disease history (Montreal classification) and Crohn's Disease surgical history will be summarized separately as well.

7.2 Medical History

Medical history data will be coded using the Medical Dictionary for Regulatory Activities (MedDRA). The actual version of the MedDRA coding dictionary will be noted in the statistical tables and clinical study report. The number and percentage of subjects in each medical history category [by MedDRA system organ class (SOC) and preferred term (PT)] will be summarized overall and by treatment group. The SOC will be presented in alphabetical order, and the preferred terms will be presented in alphabetical order within each SOC. Subjects reporting more than one condition/diagnosis will be counted only once in each row (SOC or PT).

7.3 Prior and Concomitant Medications

Prior and concomitant medications will be summarized by generic name (ITT1 and ITT2 population for prior medications; ITT1, ITT2 and ITT3 populations for concomitant medications). A prior medication is defined as any medication taken prior to the date of the first dose of study drug in Part1 or Part 2.

A concomitant medication for Part 1/Part 2 is defined as any medication other than study drug that (1) was started prior to the first dose study drug in Part 1/Part 2 and continued to be taken after the first dose of study drug in Part 1/Part 2, or (2) was started after the first dose of study drug in Part 1/Part 2, but (i) prior to the first dose of study drug in Part 3 (if applicable), or (ii) prior to the first dose of study drug of M14-430 (if applicable), or (iii) within the last dose + 30 days, whichever is earlier.

A concomitant medication for Part 3 is defined as any medication other than study drug that (1) was started prior to the first dose of study drug in Part 3 and continued to be taken after the first dose of study drug in Part 3 or (2) was started after the first dose of study drug in Part 3, but (i) prior to first dose of M14-430 (if applicable), or (ii) last dose + 30 days, whichever is earlier.

The number and percentage of subjects taking medications will be summarized by generic drug name based on the World Health Organization (WHO) Drug Dictionary for both prior and concomitant medications.

8.0 Handling of Potential Intercurrent Events for the Primary and Key Secondary Endpoints

Potential intercurrent events considered in the Study M14-431 include 1) premature discontinuation of study drug and 2) initiation or dose escalation of CD-related corticosteroids defined in Section 8.2. As suggested by Qu et al. (2021), a mix of strategies will be used to handle different intercurrent events for the efficacy analysis.

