**CD Related**

24. Subject with the following ongoing known complications of CD:
  - abscess (abdominal or peri-anal),
  - symptomatic bowel strictures,
  - > 2 entire missing segments of the following 5 segments: terminal ileum, right colon, transverse colon, sigmoid and left colon, and rectum,
  - fulminant colitis,
  - toxic megacolon,

- or any other manifestation that might require surgery while enrolled in the study.
25. Subject with ostomy or ileoanal pouch.
  26. Subject diagnosed with conditions that could interfere with drug absorption including but not limited to short gut or short bowel syndrome.
  27. Subject with surgical bowel resection within the past 3 months prior to Baseline, or a history of > 3 bowel resections.

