#### **5.5.4 Selection and Timing of Dose for Each Subject**

Subjects should take study drug as outlined in Section 5.5.1.

On dosing days that occur on study visit days, subjects should follow the regular dosing schedule (refer to Section 5.3.2.1 regarding Week 4 visit).

Each subject's dosing schedule should be closely monitored by the site at each study visit. This will ensure that all subjects enrolled into the study maintain their original dosing schedule beginning with the first dose of study drug (Baseline/Day 1).

If a subject should forget to take their upadacitinib (or matching placebo) dose at their regularly scheduled dosing time, they should take the forgotten dose as soon as they remember the dose was missed as long as it is at least 10 hours before their next scheduled dose. If a subject only remembers the missed dose within 10 hours before next scheduled dose, the subject should skip the missed dose and take the next dose at the scheduled time.

For elective and emergency surgeries, the following rules apply:

- If the subject must undergo emergency surgery, the study drug should be interrupted at the time of the surgery. After emergency surgery, allow reintroduction of study drug once the physician has examined the surgical site and determined that it has healed and there is no sign of infection.
- Elective surgery will not be allowed during the study until the primary endpoint has been assessed. If the subject undergoes elective surgery, the study drug should be interrupted 1 week prior to the planned surgery. Reintroduction of study drug is allowed once the physician has examined the surgical site and determined that it has healed and there is no sign of infection.

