- Colonic and Ileal Global Histologic Disease Activity Score (CGHAS/IGHAS) histologic remission (defined as CGHAS/IGHAS score ≤ 2) at Week 12 in subjects with abnormal histology at Baseline
- $\geq 50\%$ reduction in draining fistulas at Week 12 (population: ITT subjects with draining fistulas at Baseline)
- resolution of draining fistulas at Week 12 (population: ITT subjects with draining fistulas at Baseline)
- at least 50% decrease from Baseline in the number of days with very soft or liquid stools (Type 6 or 7, per Bristol Stool Chart) during the last 7 days at Week 12
- IBDQ remission (IBDQ ≥ 170 points) at Week 4, Week 12
- IBDQ response (increase in IBDQ ≥ 16 points from Baseline) at Week 4, Week 12

- response in IBDQ fatigue item (increase of IBDQ fatigue item score ≥ 1) at Week 4, Week 12
- response in IBDQ Bowel Symptom domain (increase of IBDQ bowel symptom domain score ≥ 8) at Week 12
- increase in FACIT-Fatigue total score from baseline ≥ 7 at Week 12
- increase in FACIT-Fatigue total score from baseline ≥ 9 at Week 12
- increase in FACIT-Fatigue total score from baseline ≥ 11 at Week 12
- resolution of EIMs at Week 2, Week 4, Week 8 and Week 12 (population: ITT subjects with EIMs at Baseline)
- Occurrence of:
 - hospitalizations during the 12-Week Double-Blind Induction Period (Part 1)
 - CD-related surgeries during the 12-Week Double-Blind Induction Period (Part 1)
- Change from Baseline in:
 - IBDQ at Week 4, Week 12
 - individual IBDQ domain scores (bowel, emotional, social, systemic) at Week 4, Week 12
 - individual IBDQ item under Bowel Symptom domain (for Q1, Q5, Q9, Q13, Q17, Q20, Q22, Q24, Q26, and Q29) at Week 4, Week 12
 - Work Productivity and Activity Impairment Questionnaire-Crohn's Disease (WPAI-CD) at Week 4, Week 12
 - European Quality of Life 5 Dimensions 5 level version (EQ-5D-5L) at Week 4, Week 12
 - Short Form-36 (SF-36) at Week 4, Week 12
 - Crohn's Symptoms Severity Questionnaire (CSS) at Week 4, Week 12
 - fecal calprotectin (FCP) at Week 4, Week 12
 - high sensitivity C-reactive protein (hs-CRP) at Week 2, Week 4, Week 8 and Week 12
 - average daily AP score at Week 2, Week 4, Week 8 and Week 12
 - average daily very soft/liquid SF at Week 2, Week 4, Week 8 and Week 12

- average daily total SF at Week 2, Week 4, Week 8 and Week 12
- CDAI at Week 2, Week 4, Week 8 and Week 12
- SES-CD at Week 12
- CGHAS/IGHAS at Week 12 among subjects with abnormal histology at Baseline
- FACIT-F at Week 4 and Week 12

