8.1 Intercurrent Event 1 (IE1): Premature Discontinuation of Study Drug

Following the intent-to-treaty (ITT) principle, a treatment policy strategy will be used to handle the IE1. Data collected on/after premature discontinuation of study drug will be used for all efficacy endpoints.

The only exception is when data are collected on/after the date subjects switching to other treatment for CD, which will be handled as follows:

- **Binary endpoints other than the occurrence of hospitalization and/or the occurrence of CD-related surgery endpoints:** A composite strategy will be used in the efficacy analysis: the subject will be considered as non-responders at all visits on/after the initiation of other CD-related confounding medications.
- **Binary endpoints regarding the occurrence of hospitalization and/or the occurrence of CD-related surgery endpoints:** A treatment policy strategy will be used regardless.
- **Continuous endpoints:** A hypothetical strategy will be used in the efficacy analysis. Data collected on/after the initiation of other CD-related confounding medications will not be used in the analysis. Efficacy analysis will be handled by using corresponding statistical models (e.g., the Mixed-Effect Model Repeated Measurement [MMRM] model).

The CD-related confounding medications include:

- Biologics approved for CD (Adalimumab, Certolizumab, Infliximab, Ustekinumab, Vedolizumab, Natalizumab)
- Any investigational compound
- Systemic corticosteroids or locally acting steroids, rectal corticosteroid
- Immunosuppressants (azathioprine, mercaptopurine, methotrexate, tacrolimus, cyclosporine)

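### CD-related surgery in Part 1 has no intercurrent-event or non-response rule, so a few operated subjects could be scored as Week 12 responders on post-surgery data

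*SAP*

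**What the plan says.** SAP 8.0 limits the intercurrent events to two: "Potential intercurrent events considered in the Study M14-431 include 1) premature discontinuation of study drug and 2) initiation or dose escalation of CD-related corticosteroids".

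For the first, SAP 8.1 takes a treatment policy approach: "Data collected on/after premature discontinuation of study drug will be used for all efficacy endpoints". It then adds: "The only exception is when data are collected on/after the date subjects switching to other treatment for CD". The rule that carries out this exception for binary endpoints is narrower, since it refers only to drugs: "the subject will be considered as non-responders at all visits on/after the initiation of other CD-related confounding medications". The list beneath it covers biologics, investigational compounds, corticosteroids and immunosuppressants. SAP 8.2 covers corticosteroids only.

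Surgery enters Section 8 only as an outcome. "Binary endpoints regarding the occurrence of hospitalization and/or the occurrence of CD-related surgery endpoints" are handled by treatment policy throughout. CD-related surgery in Part 1 is a non-ranked endpoint in SAP 3.3.1.

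Protocol 5.5.4 provides for surgery on study: "After emergency surgery, allow reintroduction of study drug once the physician has examined the surgical site" and found it healed and free of infection. The same section bars elective surgery until the primary endpoint has been assessed. Exclusion criterion 24 (Protocol 5.2.2) removes subjects with abscess, symptomatic stricture, fulminant colitis, toxic megacolon or any other manifestation that might lead to surgery during the study.

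**The concern.** An operation for Crohn's disease during induction is ordinarily a treatment failure. It can also remove or bypass the bowel that SES-CD scores, and change the stool frequency and pain that drive clinical remission. If post-surgery data are used as they stand, the failure can be recorded as a success on either co-primary endpoint and on most ranked binary endpoints.

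The plan is also uneven. Starting a corticosteroid makes a subject a non-responder from that date, and a resection does not. At entry the protocol treats recent resection as disqualifying ("Subject with surgical bowel resection within the past 3 months prior to Baseline, or a history of > 3 bowel resections"), but the same event after baseline has no analysis rule. One subject could be counted in the CD-related surgery endpoint and as an endoscopic responder at the same visit.

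**Working it through.** **1. Does any rule catch an operated subject who has Week 12 data?** The non-response triggers in SAP 9.2.1 are:

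- Evaluation missing for a reason other than COVID-19: not met, because the evaluation exists.
- Corticosteroid intercurrent event (8.2): not met unless corticosteroids were started or raised.
- Confounding medication after stopping study drug (8.1): not met, because surgery is not a listed medication.

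Tables 1 and 2 add no trigger, and the endpoint definitions in SAP 3.0 carry no surgery condition. Surgery is not itself a listed reason for stopping study drug in Protocol 5.4.1. Confirmed gastrointestinal perforation is, apart from appendicitis or mechanical injury. The subject is therefore scored on post-surgery data.

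**2. Does a planned sensitivity analysis expose it?** No.

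- NRI-NC changes only the handling of COVID-19 missingness.
- The tipping point analysis varies only missing outcomes.
- The 9-2 approach changes only the diary window.
- The as-observed analysis uses all collected data.
- Per-protocol exclusions (SAP 9.3.4) are left to a classification plan.

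**3. Can surgery alone meet the endoscopic definition?** SAP Appendix E gives values for every examined segment and has no rule for one resected after baseline. Take assumed scores: baseline SES-CD 8 (ileum) + 3 (right colon) + 1 (transverse colon) = 12. If ileum and right colon are resected and add nothing, and the rest is unchanged, Week 12 SES-CD = 1. The fall is (12 − 1)/12 = 92%, which meets the definition of more than 50%. If the resected segments instead made the total missing, the subject would be a non-responder. The outcome depends on a rule that is not written.

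**4. The plan's own figures.** Inputs from SAP 2.4: 165 placebo and 330 upadacitinib; two-sided 0.05; Fisher's exact test; planned rates 10% v 25% (endoscopic response), 12% v 29% (PRO remission), 20% v 40% (CDAI remission). Exact Fisher power is 98.7%, 99.4% and 99.6%, so the stated figure of at least 95% holds.

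Normal approximation: power = Φ[(p1 − p0 − 1.96·SE0)/SE1], where SE0 = √[p̄(1 − p̄)(1/165 + 1/330)] and SE1 = √[p0(1 − p0)/165 + p1(1 − p1)/330]. For endoscopic response, p̄ = (16.5 + 82.5)/495 = 0.20, SE0 = 0.0381, SE1 = 0.0334, z = (0.15 − 0.0747)/0.0334 = 2.25, power 98.8%.

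**5. Size of the effect.** One miscounted subject moves placebo by 1/165 = 0.61 points or upadacitinib by 1/330 = 0.30 points. The documents give no surgery rate, so the rates below are assumptions. The planned rates are taken as those with surgery counted as non-response, and miscounted subjects are added to them.

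Modest case: 1% placebo and 0.5% upadacitinib operated on, half scored as responders. Endoscopic rates become 10 + 0.5 = 10.5% and 25 + 0.25 = 25.25%, a difference of 14.75 points.

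Extreme cases, with every operated subject scored as a responder (difference in points, approximate power):

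| Operated, placebo / upadacitinib | Endoscopic | PRO | CDAI |
|---|---|---|---|
| none miscounted | 15, 98.8% | 17, 99.5% | 20, 99.7% |
| 1% / 1% | 15, 98.4% | 17, 99.3% | 20, 99.6% |
| 3% / 1% | 13, 93.2% | 15, 96.7% | 18, 98.4% |
| 1% / 3% | 17 | 19 | 22 |

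For 3% / 1% (about 5 and 3 subjects), endoscopic: p̄ = (21.45 + 85.8)/495 = 0.2167, SE0 = 0.0393, SE1 = 0.0356, z = (0.13 − 0.0770)/0.0356 = 1.49, power 93.2%. Power is omitted from the last row because any gain there would be an artefact of miscounting.

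**The case against.** The strongest case against is that this will hardly ever matter. Elective surgery is barred before the primary endpoint and criterion 24 removes the likeliest candidates, so what remains is mainly emergency surgery or a protocol deviation. Several conditions must then hold together: a Week 12 evaluation, no corticosteroid event, no confounding drug after stopping, and scores that meet the definitions. An admission for CD surgery would also count in the ranked endpoint of hospitalization due to CD, so the failure is not invisible. Treatment policy is a legitimate strategy, and the SAP uses it for drug discontinuation. All of this stands, and it limits the size of the problem. It does not supply a rule, and treatment policy for surgery is never stated as a choice.

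Two passages might be thought to close the gap. The opening words of the SAP 8.1 exception, about other treatment for CD, could include an operation, but the rule and list that follow are confined to medications. Protocol 8.1.6.1 counts anyone who discontinues before Week 12 as not achieved. It does not say whether that means study drug or study, an interruption with restart is not a discontinuation, and SAP 8.1 uses data collected after study drug is stopped. That conflict should be settled in its own right.

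A reader might infer that the gap biases the trial in favour of upadacitinib. The documents do not support that. If surgery is commoner on placebo, as one would expect of the less effective arm, the gap dilutes the effect; it flatters upadacitinib only if surgery is commoner there. Nor do they support saying that any resected subject will be an endoscopic responder, since the scoring of a resected segment is unstated.

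**Conclusion.** The omission is certain from the text. Its consequence is conditional and probably small: it concerns subjects with emergency CD surgery who reach a Week 12 evaluation without meeting another non-response trigger. The modest assumption costs a quarter of a point on the endoscopic difference. Power falls below the stated 95% only for endoscopic response, and only under the assumed extreme of 3% v 1% with every operated subject scored as a responder. The sample size is not in question.

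The main reason to act is coherence. The primary estimand should not treat a corticosteroid start as failure while leaving an operation for the same disease to be scored on whatever follows. The change should be made, but it is not a threat to the trial's main conclusion. The omission itself can be stated with high confidence. The size and direction cannot, because the documents give no surgery rate and no scoring rule for resected segments.

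**What to change.** In SAP 8.0, 9.2.1 and Tables 1 and 2, with matching words in the estimand statements of 2.1:

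- Add CD-related surgery, as captured for the SAP 3.3.1 endpoint and with its date, as a third intercurrent event.
- For binary endpoints other than occurrence of hospitalization or surgery, use the composite strategy: non-responder at all visits on or after the surgery date, not overwritten by multiple imputation or tipping-point imputation.
- For continuous endpoints, do not use data on or after that date, as is already done for corticosteroid events.
- Keep treatment policy for the occurrence endpoints.
- In Appendix E, state how SES-CD is scored when a segment is resected after baseline.
- Reconcile Protocol 8.1.6.1 with SAP 8.1 on discontinuation before Week 12.

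The cost is SAP wording and one dated derivation flag. Two checks come first. Protocol Appendix E says that numbers of hospitalizations and surgeries are collected on the SAE supplemental page but does not mention date or procedure type, so confirm that the date is available. The SAP does not define CD-related surgery, and Protocol 5.2.3.2.1 permits setons, so the definition should say which procedures count. The downside is small: a few subjects become non-responders.
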